3.0 STUDY POPULATION

3.1 SELECTION OF THE STUDY POPULATION

Patients for this study will be drawn from the orthopedic trauma service. The majority of patients with these injuries will be approached in the inpatient setting, as they present through the emergency department. A small subset does present through clinic. All patients will be recruited to participate in the study after their femoral or tibia fracture repair.

3.2 INCLUSION CRITERIA

- 18 years old and above
- Undergoing intramedullary fixation of femur or tibia shaft for acute fracture or nonunion

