3.5 SUBJECT RECRUITMENT

Patients will be recruited from all full-time orthopaedic trauma faculty. The treating surgeon and/or clinical research associate will approach patients in person to recruit, enroll and consent them for the study. No advertisement will be used for this study.

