4.0 STUDY DESIGN AND METHODS

This study will be a prospective, randomized control trial. Patients will be randomized to perform distal interlock screen insertion either by freehand or distal targeting for all lower extremity nails.

1. All patients undergoing femoral or tibial nailing will undergo one method of interlock placement starting on the first of the month starting with free-hand locking. The method of interlocking screw placement will then switch to jig-based screw placement at the first of the following month. The method of screw placement will alternate each week until enrollment is complete. This method of enrollment for clinical modalities that are already in common use has previously been described with the PREP-IT trials. [Slobogean et al, JAMA Netw Open 2020]
2. Due to the nature of the distal targeting jig's construction, there may be instances where its use is not possible due to interference with other surgical instrumentation, and an intraoperative decision must be made to place screws with the freehand technique. Patients randomized to the jig-based placement arm but are ultimately treated with freehand placement will be documented and reported as crossover patients (per the CONSORT framework).
3. Patients randomized to their respective groups will ultimately undergo intention-to-treat analysis.

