7.0 STATISTICAL CONSIDERATIONS

7.1 STUDY OUTCOME MEASURES

- Primary Outcome analysis: 2 tailed T-test for average length of surgery (skin to skin), average time to place 2 interlocks (start time when nail is seated and surgeon states s/he is ready to proceed with distal interlocking screw placement). Average radiation used in microGrays. Femur vs tibia average time to place 2 interlocks and average radiation exposure.
 - To compare time and accuracy of placement only data from surgeons who have performed both DT and FH techniques more than 5 times will be included.
- Secondary outcomes: t-test accuracy of screw placement (perpendicular to nail)
 - Multivariate regression evaluating predictors of time to placement
 - Level of training
 - Number of cases performed
 - Number of interlocking screws placed
 - Time since last case
 - Learning curve assessment
 - Time of each interlocking screw placement will be correlated with number of interlocking screws placed
 - Time of procedure and accuracy of placement will be analyzed in increments of 5 cases to evaluate for number of cases required to reach plateau
 - Data will be stratified by level of training

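### Technique follows a predictable calendar, and skin-to-skin length of surgery is compared without adjustment for acute fracture versus nonunion

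*Combined protocol and SAP*

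**What the plan says.** - **Eligibility (3.2).** One criterion covers both diagnoses: "Undergoing intramedullary fixation of femur or tibia shaft for acute fracture or nonunion". No stratification by diagnosis is described. Section 3.3 excludes patients with an earlier nail in the same limb's tibia or femur.
- **Allocation (4.0).** The design is described thus: "This study will be a prospective, randomized control trial". The rule itself is a calendar: "All patients undergoing femoral or tibial nailing will undergo one method of interlock placement starting on the first of the month". Free-hand locking comes first, the jig follows from the first of the next month, and then "The method of screw placement will alternate each week until enrollment is complete". No random sequence or concealment is described. The monthly and weekly statements need to be reconciled, but the arm is predictable under either. Analysis is by intention to treat.
- **Route of entry (3.1).** Most patients come through the emergency department. Of the others it says "A small subset does present through clinic".
- **Analysis (7.1).** The first item under the primary analysis is a "2 tailed T-test for average length of surgery (skin to skin"), with no covariates. The only regression is secondary. It models time to placement, and its listed predictors are training and experience variables, not diagnosis.
- **Data (5.3).** Type of injury is collected. No analysis uses it.

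**The concern.** A calendar rule gives some quasi-random protection when the operation date is driven by when the patient arrives. That protection weakens for any case that can be brought forward or put back, because whoever moves the date also moves the arm. Under the weekly wording, a shift of one week is enough. Nonunions are plausible candidates for such movement.

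Intention-to-treat analysis keeps patients in the arm to which the calendar assigned them. It has no effect on how they came to be operated on in that period.

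Skin-to-skin time is the listed outcome most open to this, because it includes all the work of the operation and not only distal locking. If diagnosis affects total operating time and the mix of diagnoses differs between arms, the unadjusted difference in means combines the effect of technique with the effect of case mix. If the mix happens to be equal, diagnosis still adds noise that the plan could remove with a variable it already intends to collect.

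**Working it through.** **1. The plan's own figure (7.2).** Inputs: means of 616 s and 344 s, SD 192 s, two-sided 5%, 90% power.
- Difference: 616 − 344 = 272 s = 4.53 min (272/616 = 44%).
- The normal-approximation formula gives 11 per technique arm, so 22 per bone cohort.
- 22/0.75 = 29.3, rounded up to 30 per cohort. Two cohorts make 60, and 60/0.91 = 65.9, rounded up to 66.

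The stated 30, 60 and 66 are reproduced if a cohort means a bone and the 30 already allows for 75% participation. The calculation concerns locking time. No power basis is given for skin-to-skin time.

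**2. Shift from unequal shares.** Let L be the extra minutes for a nonunion operation, n the number per technique, and k₁ and k₀ the nonunion counts in the two arms:

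shift in mean difference = L × (k₁ − k₀)/n

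Assume n = 30 (60 patients split evenly by technique) and L = 60 min, range 30 to 90. Neither L nor the nonunion share is in the documents.
- One net extra nonunion: 30/30 = 1 min, 60/30 = 2 min, 90/30 = 3 min.
- A deliberately uneven example, with 9 nonunions (15% of 60, assumed) split 7 to 2 and L = 60: 60 × 5/30 = 10 min.

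**3. Effect on type I error.** Assume a skin-to-skin SD of 40 min, 33 per technique (66/2) and no true effect. Simulated t-test, 40,000 repeats:

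| Nonunion share by arm | Extra 30 min: bias, error | Extra 60 min: bias, error | Extra 90 min: bias, error |
|---|---|---|---|
| 10% and 10% | 0 min, 5.0% | 0 min, 5.0% | 0 min, 5.0% |
| 15% and 5% | 3 min, 6.0% | 6 min, 8.6% | 9 min, 11.2% |
| 20% and 0% | 6 min, 8.9% | 12 min, 19.5% | 18 min, 32.4% |

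**4. Variance when shares do not differ systematically.** With common share p, diagnosis adds an SD of L × √(p(1 − p)) and contributes that SD × √(2/n) to the standard error of the difference.
- p = 0.15, L = 60: SD = √(0.15 × 0.85 × 60²) = 21.4 min; contribution at n = 30 is 21.4 × √(2/30) = 5.5 min.
- p = 0.05, L = 30: SD = √(0.05 × 0.95 × 30²) = 6.5 min; contribution 1.7 min.

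**5. Which outcomes are exposed.** Section 2.0 times each interlock from the first localising fluoroscopy shot to the shot confirming that the screw is seated. Section 7.1 starts the clock once the nail is seated. Work done earlier in the operation falls outside both windows, so locking time is largely shielded. The radiation window is not defined in 7.1, so its exposure depends on whether the whole case is measured.

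**The case against.** The strongest reply is that much of this is possibility rather than plan.

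- **Who sets the date.** A reader might infer that the surgeon schedules nonunion surgery and so chooses the arm. The documents do not say so. On the surgeon's role, section 3.5 states only that "The treating surgeon and/or clinical research associate will approach patients in person to recruit, enroll and consent them for the study", and nothing says who books operations or that nonunion surgery is elective. What stands is an opportunity for anyone able to move a date.
- **Longer operations.** No section says that nonunion operations take longer. Even if they do, length alone does not bias the comparison; it does so only when the shares differ.
- **Small subset.** Only a few patients come through clinic, and the exclusion of earlier ipsilateral nails removes some nonunions. The group may be very small, but section 3.2 expressly keeps it eligible.
- **Size.** It is tempting to set the 1 to 3 min shift against the planned 4.5 min saving (22% to 66% of it) and conclude that a modest imbalance could create or hide the whole effect. The 4.5 min is an effect on locking time, so the ratio crosses endpoints, and the larger shifts need the more extreme assumed splits.
- **Radiation.** Nothing in the documents establishes that radiation is measured over the whole case, so it cannot be counted as affected without that definition.
- **Root cause.** The underlying weakness is predictable calendar alternation described as randomization, and adjusting for diagnosis leaves it in place. That is correct. The adjustment is still worthwhile if the calendar rule is kept.

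**Conclusion.** The point holds in a limited form. The documents establish that the arm is predictable from the operation date, that nonunions are eligible alongside acute fractures, that skin-to-skin time is listed under the primary analysis with an unadjusted test, and that type of injury is collected but not used.

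If nonunion operations are 30 to 90 min longer, each net extra nonunion in one arm of 30 shifts the mean difference by 1 to 3 min. With no systematic imbalance, the cost is precision only. The extra time, the nonunion share, the skin-to-skin SD and the even split by technique are all assumptions, so the true size is unknown and could be trivial. The powered outcome, distal locking time, is much less affected. The documents do not support a claim that surgeons choose the arm or that the trial's main result is overturned.

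**What to change.** - **7.1, length of surgery.** Replace the unadjusted t-test with a linear model containing technique, acute fracture versus nonunion, and bone (femur or tibia). Report the adjusted technique difference with its confidence interval.
- **7.1, radiation.** State the measurement window. If it is the whole case, use the same model.
- **7.1, sensitivity analysis.** Repeat the technique comparison in acute fractures only.
- **5.3.** Define type of injury so that it records acute fracture versus nonunion. The present entry does not say whether it does.

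The cost is one or two degrees of freedom, a clarified data field and slightly more analysis work.

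Two alternatives are less attractive. Restricting every primary comparison to acute fractures would drop patients from the locking-time analysis, where the extra work barely enters. Fixing the technique when eligibility is confirmed in clinic would still be predictable, and it does not fit section 3.1, which describes recruitment after the repair.

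The adjustment deals with differences in diagnosis only. It does not correct selection on difficulty or preference within a diagnosis, and the predictable calendar allocation in 4.0 remains a separate matter for the sponsor to address.

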3.3 EXCLUSION CRITERIA

- Prior ipsilateral tibial or femoral nail
- Patients who cannot have interlocking screws placed
- Pregnant patients
- For sub-study only: retrograde nails

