1.0 BACKGROUND, RATIONALE

Background: Interlocking screw placement in intramedullary nailing of femoral and tibial shaft fractures improves rotational and length stability. However, free-hand perfect circle techniques can be technically challenging and may take up to an hour with increased radiation exposure to the surgeon and patient (Whatling et al, Injury 2006). Newer technologies aimed at reducing fluoroscope use such as electromagnetically-based aiming devices may increase operative time (Maqungo et al, JOT 2014). Proximally-based jigs have been shown to reduce fluoroscopy time in cadavers (Miclau et al, Arch Orthop Tr Surg 1998), however have not been studied clinically.

We propose a prospective, randomized controlled trial comparing a modern proximally-based distal targeting device and free-hand techniques for placement of interlocking screws in lower extremity nailing.

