2.0 STUDY OBJECTIVES

Outcomes:

- Primary outcomes: radiation exposure, time, accuracy of placement (right angle to rod).
 - Each distal interlock will be considered a separate outcome
 - The first fluoroscopy shot to localize the jig or obtain a perfect circle is considered start time. The surgeon will note the hour, minute, and seconds of the time based on the wall clock in the operating room.
 - The last shot to confirm complete seating of the screw will be considered end time. The surgeon will note the hour, minute, and seconds of the time based on the wall clock in the operating room.
- Secondary outcomes:
 - accuracy of placement (right angle to intramedullary nail).
 - Number of complete misses of the nail with the drill or the screw
 - comparison of learning curve between distal targeter and freehand techniques stratified by level of training
 - The level of training of the surgeon
 - Experience level of the surgeon
 - estimated number total number of intramedullary nails placed
 - time since the last intramedullary nail placement
 - estimated number of nails placed per month over the last year
 - number of times the surgeon has used the distal targeting system
 - Comparison of tibia vs femur antegrade nails

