3.4 SUBJECT SCREENING AND ENROLLMENT

Data for this study will be collected prospectively, as the patients are admitted, and assessment of their injuries matches our inclusion and exclusion criteria. Radiographic imaging from medical records will be reviewed for the purposes of screening or contacting prospective subjects. The primary investigator and

Clinical Research Associate will access the records needed for screening from CS-Link, a HIPAA compliant electronic medical records system.

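### The exclusion for patients who cannot have interlocks placed has no time point, and an interlock that is never seated has no time value, so never-completed locking can drop out of the time comparison

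*Combined protocol and SAP*

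**What the plan says.** Section 3.3 lists as an exclusion "Patients who cannot have interlocking screws placed". It does not say when this is judged, by whom or on what evidence.

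The documents point two ways on timing. Section 3.4 reads as screening on arrival: "Data for this study will be collected prospectively, as the patients are admitted, and assessment of their injuries matches our inclusion and exclusion criteria". Section 3.1 says: "All patients will be recruited to participate in the study after their femoral or tibia fracture repair". Under section 3.5 the treating surgeon may be the one who approaches the patient.

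On measurement, section 2.0 starts the clock as follows: "The first fluoroscopy shot to localize the jig or obtain a perfect circle is considered start time". It stops it thus: "The last shot to confirm complete seating of the screw will be considered end time". Section 7.1 analyses a two-screw time by t-test with a different start and no stated end: "average time to place 2 interlocks (start time when nail is seated and surgeon states s/he is ready to proceed".

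On the analysis set, section 4.0 says: "Patients randomized to their respective groups will ultimately undergo intention-to-treat analysis". It also keeps jig patients who are converted to freehand and reports them as crossovers. Section 2.0 counts complete misses of the nail as a secondary outcome.

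**The concern.** Whether an interlock can be placed is partly a result of the techniques being compared. An exclusion worded around that result, with no date attached, can remove a patient because of the outcome. The technique follows the calendar (section 4.0), so it is known throughout. If recruitment follows the repair, the locking result is known as well.

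The clock rule leaves a second gap, which does not depend on how the exclusion is read. A patient who stays in the trial but has an interlock abandoned has no confirming shot and so no end time. The t-test on time to place two interlocks cannot use that patient.

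At stake is the outcome on which the trial is powered. If never-completed locking is more common with one technique, that arm loses attempts that would probably have been among its slowest, and the comparison of means shifts in its favour.

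**Working it through.** **1. The plan's own figure.** Section 7.2 gives means of 616 s and 344 s, SD 192 s, 90% power and 5% significance; section 7.1 makes the test two-sided.

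- Difference: 616 − 344 = 272 s; 272/616 = 44.2%, matching the stated 44%.
- Per technique: n = 2 × (1.960 + 1.282)² × 192²/272² = 10.5, so 11. A t-based calculation gives 11.5, so 12.
- Per bone cohort: 2 × 11 = 22; 22/0.75 = 29.3, so 30. Two cohorts give 60; 60/0.91 = 65.9, so 66.

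The stated 30, 60 and 66 reproduce, although the route through 22 per cohort is inferred. Normal-approximation power is 91% at 11 per technique and 97% at 15. The issue here is bias, not power.

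**2. Tracing each kind of case through the text.**

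| Case | Time under 2.0 | Status |
|---|---|---|
| Slow placement, screw seated | Yes | Kept |
| Repeated misses, then seated | Yes | Kept; misses also counted |
| Jig converted to freehand, screw seated | Yes | Kept as crossover, by intention to treat |
| Locking never completed, judged an exclusion after surgery | None | Whole patient lost |
| Locking never completed, patient kept | None | Time lost; radiation and length of surgery still available |

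Only the last two rows are at risk. Intention to treat fixes the group in which a patient is counted. It neither supplies a missing time nor restores a patient who was never enrolled.

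**3. Illustration of size.** The documents give no rate of failed locking, so the loss shares q below are assumptions. Further assumptions are normal times with SD 192 s in each arm and that the lost attempts are the slowest. With z the upper-q normal quantile and φ the normal density, losing the slowest share q lowers an arm's mean by 192 × φ(z)/(1 − q):

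- q = 5%: 192 × 0.1031/0.95 = 21 s
- q = 10%: 192 × 0.1755/0.90 = 37 s
- q = 20%: 192 × 0.2800/0.80 = 67 s

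| Loss in one arm only | Freehand loses: difference | Jig loses: difference | Rejection rate if no true difference |
|---|---|---|---|
| 5% | 251 s | 293 s | about 6% |
| 10% | 235 s | 309 s | about 9% |
| 20% | 205 s | 339 s | about 18% |

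The last column assumes 15 per technique within a bone cohort (30 split 1:1; the allocation ratio is not stated). The shifts in the difference do not depend on arm size. As shares of 272 s they are 21/272 = 8%, 37/272 = 14% and 67/272 = 25%.

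Equal loss of 5% or 10% in both arms leaves the difference at 272 s under this model and only lowers the SD, to 173 s or 162 s.

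**The case against.** The strongest reply is that the exclusion is a patient characteristic. Section 3.4 screens from injuries and imaging at admission, and on that reading nobody is removed because a screw failed. This is a fair reading and may be the intended one. Section 3.1 does not allow it to be taken as settled, and it does nothing for the missing end time.

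A second reply is that the plan already foresees technique failure: crossovers are kept, misses are counted, and section 2.0 treats each distal interlock as its own outcome, so one failed screw need not remove the other from a per-screw analysis. This stands for what it covers. It does not cover freehand locking that is abandoned, or locking that fails by both methods, and section 7.1 analyses two interlocks together.

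Three stronger inferences are tempting and should be resisted.

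- A reader might infer that each technique's worst results drop out. They do not: long or difficult placements that end in a seated screw have an end time and remain.
- A reader might take the remark in section 1.0 that freehand placement "may take up to an hour with increased radiation exposure to the surgeon and patient" and compute that losing one 3600 s case from 33 freehand patients moves the mean by (3600 − 616)/33 = 90 s. That remark describes how long placement can take, not an abandoned attempt, and a screw seated after an hour would be timed and kept. The 33 per technique is also an assumption (66/2).
- A reader might infer that the highest radiation values vanish too. Radiation and length of surgery are collected under section 5.3 and need no seated screw. They are lost only if the patient is excluded outright.

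**Conclusion.** The concern holds in a narrow form. As written, a patient whose locking is never completed can be excluded after technique and result are known or, if kept, has no value for the powered time outcome. Nothing in the plan resolves either case.

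The documents do not show that such exclusions are planned, how often locking fails, or which technique would be favoured. Bias in the difference needs unequal loss. Under the stated assumptions, one-sided loss of the slowest 5-20% would move the 272 s difference by about 21-67 s, downward if freehand loses cases and upward if the jig does. These figures illustrate scale and are not estimates. The sample size is not in error.

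The point is worth acting on because the direction cannot be known in advance, and an abandonment time that was not recorded cannot be reliably recovered later.

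**What to change.** - **Eligibility.** Reword section 3.3 so that the exclusion is judged before incision and without regard to the locking result, and reconcile section 3.1 with section 3.4 on when patients are recruited.
- **Analysis set.** State in section 4.0 that every allocated patient stays in the intention-to-treat set, including for radiation and length of surgery, whether or not locking is completed.
- **Reporting.** Report never-completed interlocks by arm.
- **Time analysis.** Record the time at which an attempt is abandoned, but do not enter it as an ordinary completion time, because giving up early would then score as fast locking. Either censor at that time or assign a worst rank, for example in a rank-based sensitivity analysis beside the t-test, and choose before the data are seen. State how a patient with only one of two interlocks seated is handled.
- **Clock.** Use one start-time definition in sections 2.0 and 7.1, and give section 7.1 an end.

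The cost is a few sentences of wording, one extra recorded time in the affected cases and one added sensitivity analysis. A few long or censored values will stay in the data and may widen the spread.
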